SECONDARY OBJECTIVES	To evaluate rates of late (> 3 months after treatment) gastrointestinal toxicity following fractionated Linac based SBRT for pancreatic tumors. Toxicities of note include grade 2 or greater gastritis, enteritis, fistula, or ulcer and any other grade 3 or greater gastrointestinal toxicity. To evaluate local progression free survival, overall survival and metastasis-free survival rates after Linac based SBRT and subsequent resection in patients with resectable and/or borderline resectable pancreatic adenocarcinoma of the head and/or body. To develop and standardize Linac based SBRT delivery and dosimetric parameters. To estimate resection margin positivity (R0/R1) and pathologic complete response rate after neoadjuvant SBRT To evaluate pre- and post- SBRT patient reported quality of life (QOL)
TREATMENT	After 3- 4 months of chemotherapy, patients will be enrolled to a single arm trial of stereotactic body radiotherapy (SBRT) in 5 fractions given over 15 days. They will then proceed to surgery after a break of 4-6 weeks.

INCLUSION CRITERIA	
 • Age >18 years. • Karnofsky Performance Status >70% (see Appendix IV). • Histologically confirmed pancreatic adenocarcinoma of the head and/or body; at least the majority of the histopathologic specimen must be identified as adenocarcinoma. • Pancreatic tumors must be considered at least borderline resectable and/or borderline resectable at time of treatment planning. Definition of resectable and/or borderline resectable: no metastases, less than 180 degree involvement of hepatic artery, superior mesenteric artery or celiac artery • No active infection requiring hospitalization • If bilirubin > 2, patients must have a biliary stent placed prior to SBRT. • Patients must have acceptable organ and marrow function (see section “Inclusion Criteria, page 17-18). • Women who are not post-menopausal (as defined in Appendix V) should have a negative urine or serum pregnancy test. Women of childbearing potential must agree to use adequate contraception for the duration of study participation. • Ability to understand and the willingness to sign a written informed consent document. • Life expectancy > 3 months. • Patients are to have received neoadjuvant chemotherapy prior to enrollment. Approved regimens may consist of 3-4 months of gemcitabine-based chemotherapy or FOLFIRINOX. Patients will have a 2-4 week break between last chemotherapy administration and start of

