not the PI believes the event to be related to the study. All other events, which are both serious and unanticipated, must be reported to the UC IRB within a time period as specified by current institutional guidelines after the PI learns of the event. Events which are serious, but anticipated, should be reported as part of the continuing review application. If any of these Serious Adverse Events requires a change to the protocol or consent form, the PI must make those changes promptly and submit the revised documents to the UC IRB. Important Adverse Events that are unanticipated must be reported to the UC IRB within a time period as specified by current institutional guidelines. If the Important Adverse Event requires changes to the protocol or consent form, the PI must make those changes promptly and submit the revised documents to the UC IRB. All other unanticipated Adverse Events or changes to the protocol and consent form must be reported to the UC IRB, within a time period as specified by current institutional guidelines.

IX. STATISTICAL CONSIDERATIONS

Study Overview

This pilot study is designed to assess the feasibility of giving neoadjuvant SBRT in resectable and/or borderline resectable pancreas cancer patients. The feasibility demonstration will establish the infrastructure for future randomized phase II clinical trials in a single or multi-center setting. Twenty patients with resectable and/or borderline resectable pancreas cancer, confirmed by multi-disciplinary radiologic review, will be enrolled and treated. The decision regarding whether this study demonstrates sufficient feasibility to support a phase II study testing novel regimens in this disease population will be based on three key considerations:

- The study can meet the accrual goal.
- The proposed preoperative SBRT will result in no more toxicity than has been established previously in the borderline resectable and locally advanced setting by evaluating the prevalence of grade 3+ toxicities and treatment delay rate (> 4 weeks).
- The completion rate of preoperative and operative therapy meets the goals.

Sample Size

A maximum of 20 patients will be enrolled if the trial completes accrual.

Accrual time

The anticipated monthly accrual rate is approximately 1-2 patients per month. The trial is expected to accrue in approximately 24 months.

Statistical Design for Primary Endpoints

Primary Endpoints

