All late AE and the maximum grade for each type of adverse events (including all adverse events and those that are possibly, probably or definitely related to study treatments) will be recorded for each patient. The frequency tables will be reviewed to determine the patterns. Point estimate and confidence interval will be reported for binary endpoints. All patients meeting the eligibility criteria and confirmed by central review who have signed a consent form and have begun any dose of treatment will be evaluable for the following secondary endpoints, unless otherwise specified.

- The positive margin resection rate is defined as number of patients achieved R0 versus R1/R2 resection during surgery divided by number of evaluable patients. (R0= negative margin, R1= microscopically positive margin, R2= macroscopically positive margin). Point estimate and confidence interval of the rate will be reported.
- The histopathologic response rate is defined as number of patients achieved CR or PR determined according to histopathologic examination during pre-operative chemo or chemoradiotherapy divided by number of evaluable patients. Point estimate and confidence interval of the rate will be reported.
- Time to locoregional recurrence is defined as time from the date of registration to the date of the first documented locoregional recurrence. The Kaplan-Meier methods will be used to estimate the median time, and event-free rate at specific time points (6 month, 12 month, etc.).
- Time to distant recurrence is defined as time from the date of registration to the date of the first documented distant recurrence. The Kaplan-Meier methods will be used to estimate the median time, and event-free rate at specific time points (6 month, 12 month, etc.).
- Overall survival is defined as time from the date of registration to the date of the death due to all causes. The Kaplan-Meier methods will be used to estimate the median time, and event-free rate at specific time points (6 month, 12 month, etc.).

Safety Stopping Rules

In addition to toxicity feasibility stopping rules, accrual will be temporarily suspended to the study, if at any time, we observe events considered at least possibly related to study treatment an adverse event with attribute specified as ("possible," "probably," or "definite") that meet the following:

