- The rate of treatment-related deaths during treatment, or within the first 60 days following completion of treatment, is 2 or more in the first 10 patients, or after 10 patients, 20% or more of all treated patients.
- We will also review grade IV and V adverse events deemed "unrelated" or "unlikely to be related" to verify their attribution and to monitor the emergence of a previously unrecognized treatment-related adverse event

X. DATA REPORTING / REGULATORY CONSIDERATIONS

Study Monitoring

UCCI-GI-002

Amendment 4

Page 22

4/15/2016

This study will be monitored by the University of Cincinnati DSMB and IRB. The PI will be responsible for maintaining the clinical protocol and subjects' study charts, reporting adverse events, assuring that consent is obtained and documented, and reporting the status of the trial in continuing renewals submitted to their IRB and trial monitoring group(s) as per UC protocol. There will be password-protected limited access to the database in order to maintain privacy (See Confidentiality below).

Monitoring Plan

UCCI DSMB will conduct study audits after enrollment of each 10 patients to review subjects' timely and complete enrollment, registration into the electronic database, and follow-up per study calendar. More frequent monitoring will take place as needed. Trial monitoring with subject chart and trial binder reviews will be done by the UCCI Clinical Trials office.

Data Entry and Compilation

Subject data will be documented and stored in the electronic database Oncore, the software and infrastructure being supplied by UCCI clinical trials office. Research Staff (Coordinators, Nurse, or Co-Investigators) will enter/scan subject data into Oncore, which will include:

- Eligibility or Inclusion/Exclusion Criteria
- Patient Demographics
- Pre-Study Evaluation including H & P, Allergies, and Review of Systems
- Surgical Procedures, with dates and findings (including EUS, biopsy (if needed), seed placement, and/or stent (if recommended))
- Scan dates (pancreas protocol CT)
- Treatment planning date
- Pre-Study Labs including hematology, chemistry, and tumor markers (CBC, CMP and CA 19-9)
- Radiation therapy dates and toxicities reported
- Pre-study chemotherapy records including drugs, doses, and schedules
- Surgery records including pathology reports (pathologic staging, margin status, histology), length of hospitalization and postop complications according to Appendix VI.

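### After 10 patients, the treatment-related death rule counts patients still inside their own death window as event-free, so the interim rate is biased down and suspension can come slightly late

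*Combined protocol and SAP*

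**What the plan says.** Section IX, Safety Stopping Rules, states that "accrual will be temporarily suspended to the study, if at any time, we observe events" at least possibly related to study treatment that meet its criteria. The only numeric criterion concerns treatment-related deaths "during treatment, or within the first 60 days following completion of treatment": accrual is suspended if their rate "is 2 or more in the first 10 patients, or after 10 patients, 20% or more of all treated patients". The rule does not restrict the denominator to patients who have finished the window, does not hold accrual while patients are inside it, and does not say whether treatment ends with SBRT or with surgery.

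Timing comes from elsewhere. The Synopsis gives SBRT over 15 days and then says "They will then proceed to surgery after a break of 4-6 weeks". Section IX, Accrual time, says "The anticipated monthly accrual rate is approximately 1-2 patients per month" and also "The trial is expected to accrue in approximately 24 months". With a maximum of 20 patients, the second statement implies 20/24 = 0.83 per month.

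The Toxicity Stopping Rules in the same section work differently. They are assessed once toxicity data are available on the first 10, 15 and 20 evaluable patients.

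**The concern.** The 20% limit describes a risk over a fixed window, but the rule is applied continuously and divides by everyone treated so far. A patient who started last week adds one to the denominator and cannot yet have survived the window. The interim figure therefore understates the windowed risk, and more so the faster patients enter. The same deaths may or may not suspend accrual depending on how many later patients have started.

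This matters because it is the plan's only numeric rule for deaths. Post-operative deaths come late in the window, when more later patients are likely to have started.

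**Working it through.** **The plan's own figures.** No operating characteristic is stated for the death rule, so there is none to reproduce. Its two parts agree at the join: 2/10 = 20%.

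**Patients inside the window.** If treatment means SBRT only, the window is 15 + 60 = 75 days from the first fraction. The expected number inside is rate × 75/30.44:
- 0.83 per month: 2.1
- 1 per month: 2.5
- 2 per month: 4.9

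If treatment runs through surgery, the window is 15 + 28 + 60 = 103 to 15 + 42 + 60 = 117 days, and the number inside is 2.8 to 7.7 over the same rates.

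**Deaths needed as written.** Beyond 10 patients the number is 0.20 × number treated, rounded up: 3 deaths at 11-15 treated and 4 at 16-20 treated. Two or more deaths among patients 1-10 suspend accrual at any time.

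**Where the gap lies.** Compare this with counts by order of SBRT start: 2 in the first 10, 3 in the first 15, 4 in 20.
- Up to 15 treated, the two rules coincide.
- From 16 treated, both suspend at 4 deaths in total, and both suspend on 2 in the first 10.
- They differ only with exactly 3 deaths in total, all in the first 15, at most one of them in the first 10, and the third occurring after patient 16 has started.

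Ordered counts therefore never suspend later than the rule as written.

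**Example.** Eighteen patients are treated, the first 15 are past their windows, and deaths occurred in patients 5, 12 and 14. The rule as written gives 3/18 = 16.7%, so there is no suspension and patients 19 and 20 may enter. Among the first 15, 3/15 = 20.0%.

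**Exact ceiling on the difference.** Let p be the true treatment-related death rate (assumed). With evenly spaced entry, patients 1-10 have left the 75-day window before patient 20 starts, so the difference cannot exceed

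P(0 deaths in 10) × P(3 or more in 5) + P(1 death in 10) × P(2 or more in 5).

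- p = 0.20: 0.1074 × 0.0579 + 0.2684 × 0.2627 = 0.0062 + 0.0705 = 7.7%
- p = 0.05: 0.5987 × 0.0012 + 0.3151 × 0.0226 = 0.0007 + 0.0071 = 0.8%

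**Simulated difference.** The setting is 20 patients, p = 0.20 and a 75-day window. The outcome is the chance of suspension before patient 20 starts, with the first-10 count kept by patient. Post-operative deaths are placed uniformly on days 43-75 (15 + 28 = 43); the alternative spreads deaths over days 0-75.

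| Accrual | Deaths | As written | Ordered counts | Loss (points) |
|---|---|---|---|---|
| 0.83/month, even | days 43-75 | 70.2% | 71.6% | 1.4 |
| 1/month, even | days 43-75 | 69.7% | 71.6% | 1.9 |
| 2/month, even | days 43-75 | 65.1% | 70.0% | 4.9 |
| 2/month, even | days 0-75 | 68.2% | 70.8% | 2.6 |
| 2/month, random | days 43-75 | 65.3% | 68.6% | 3.3 |

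With deaths on days 0-75, the loss is about 0.5 points at 0.83 per month and 0.8 at 1 per month. A repeat run gave losses within about 0.1 point of all these figures and found no simulated trial in which ordered counts missed a suspension that the written rule made.

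**Cost at an acceptable rate.** At p = 0.05, 2 per month and deaths on days 43-75, suspension is 9.3% under ordered counts against 8.6% as written. This 0.7-point increase is the largest among the settings tried; it is typically about 0.2-0.6 points.

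**The case against.** The strongest reply is that the rule does what it says. The limit is defined on all treated patients, and when that figure reaches 20%, accrual is suspended. A reader might infer that accrual can continue after the protocol's own limit has been reached. The documents do not support that. What can happen is that accrual continues when deaths are 20% of an enrolment-ordered or fully followed group, which is not the quantity the plan names.

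A reader might also take the rule in stages, so that two deaths among the first 10 patients cease to count once patient 11 has started (2/11 = 18.2%). On that reading, suspension at p = 0.20 and 2 per month falls to 55% against 70%, a loss of 15 points. But the clause identifies particular patients and the rule applies at any time, so the natural reading keeps those two deaths decisive.

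Nor is 3 deaths among the first 12 patients (25%) generally missed. To escape the first-10 count, patients 11 and 12 must both have died, with one death in the first 10. That is 10 of the 220 possible placements.

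The size also depends on the comparator. If the rate is computed strictly among patients who have completed the window, suspension at p = 0.20 is 65-71% against 64-70% as written, and accrual runs on in the gap in only 0.1-1.5% of simulated trials across assumed rates of 5-30%.

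Other safeguards exist. Fatal events go to the IRB whatever their relation to the study, related grade 5 events count in the grade 3+ toxicity rule, and a DSMB monitors the trial. Suspension is also only temporary.

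These replies reduce the size and priority of the point. They do not remove the downward bias, and none of the other safeguards corrects the denominator.

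**Conclusion.** The concern holds in a limited form. After 10 patients the interim death rate is biased down by patients still in their window, but the first-10 count confines the effect to one narrow configuration. At an assumed 20% death rate, the loss in the chance of suspending before patient 20 starts is about 1-2 points at 0.83-1 per month and about 3-5 points at 2 per month. It is smaller when deaths are spread over the whole window.

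The death rate, the timing of deaths and the pattern of entry are assumptions; the documents give none of them. The 75-day window assumes that treatment ends with SBRT, which the rule does not state. Severity is minor: a cheap improvement, not a defect that undermines the trial.

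**What to change.** Keep the sponsor's 20% level and write the clause for later patients in the form already used for the first 10. Accrual is suspended as soon as there are 2 or more treatment-related deaths among the first 10 patients, 3 or more among the first 15, or 4 or more among the 20. Patients are ordered by SBRT start, regardless of how many later patients have started. These counts are exactly 20% (2/10, 3/15, 4/20) and use the same cohort sizes as the toxicity looks. Remove the all-treated denominator.

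The sponsor should also state whether treatment, for the 60-day window, ends with SBRT or with surgery.

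The change takes a sentence or two in Section IX and needs no new data or patients. Its price is slightly more temporary suspensions when the true rate is acceptable: less than one percentage point at a 5% death rate.

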--------------------	--

EXCLUSION CRITERIA	
 • Presence of metastatic disease. • Infections requiring systemic antibiotic treatment. • Unable to understand or unwilling to sign a written informed consent document. •
PROCEDURES	Endoscopically guided fiducial placement with optional biopsies obtained at the time of fiducial placement.
STATISTICAL CONSIDERATIONS	See statistics section.

SCHEMA

Eligibility: resectable or borderline resectable adenocarcinoma of the pancreas. Definition of resectable: no metastases, less than 180 degree involvement of hepatic artery, superior mesenteric artery or celiac artery

I. OBJECTIVES

Primary Objective

- To evaluate rates of acute (within 3 months of treatment) grade 3 or greater gastrointestinal toxicity.

Secondary Objectives

- To evaluate rates of late (> 3 months after treatment) grade 2 gastritis, enteritis, fistula, and ulcer, or any other grade 3 or greater gastrointestinal toxicity
- To determine rates of local progression free survival, overall survival, and metastasis- free survival in patients with resectable and/or borderline resectable pancreatic adenocarcinoma of the head and/or body undergoing neoadjuvant SBRT
- To evaluate patient quality of life before and after Linac based SBRT.
- To evaluate the margin positivity rate and pathologic complete response rate after Linac based SBRT.
- To further develop standardization of Linac based SBRT delivery and dosimetric parameters.

II. BACKGROUND

Natural History and Management of Pancreatic Cancer

More than 40,000 individuals are diagnosed with pancreatic cancer annually in the United States. Despite aggressive combined modality treatment approaches, five-year survival of patients with pancreatic cancer is still less than 5% (1). Clearly, more innovative treatments are needed to improve survival in this group of patients.

Surgical resection is considered to be the only potentially curative treatment option (2). However, the majority of pancreatic cancer patients do not have resectable and/or borderline resectable disease at presentation. More than 85% of patients have locally advanced or metastatic disease when initially diagnosed.

Current Adjuvant Management of Resectable and/or borderline resectable Pancreatic Adenocarcinoma

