Quality of life will be assessed using the European Organization for Research and Treatment in Cancer quality of life core cancer questionnaire with the pancreatic cancer module (EORTC QLQ-C30/PAN26). The EORTC QLQ-C30 is a multidimensional, 30-item questionnaire, which assesses five functional scales (physical, role, cognitive, emotional, and social), three symptom scales (fatigue, pain, and nausea/vomiting), a global health/QOL scale, as well as 6 single items (42). The EORTC QLQ-PAN26 supplements the core questionnaire with 26 items specific for patients with pancreatic cancer (43,44). These instruments have been validated in patients receiving treatment for metastatic and resected pancreatic cancer and are sensitive to identify treatment related changes in quality of life. The quality of life of patients in this study will be compared to historical cohorts of patients treated with conventional chemoradiation at University of Cincinnati and other institutions.

IV. METHODS

REGISTRATION PROCEDURES

General Guidelines

Subjects will be identified per the recommendation of Surgeons, Medical Oncologists, Radiation Oncologists or GI Combined Modality Tumor Board or equivalent combined modality assessment. Subjects will be recruited through self-referral and the advice of their attending physician. Patients will be enrolled prior to start of SBRT. Patients will have chemotherapy (3-4 months) for pancreas cancer prior to study enrollment.

Registration Process

A member of the research team (most likely the research coordinator) will enroll the patient into the trial. Consent will be obtained after a clear and thorough discussion between the patient and the principal investigator or any of the co-investigators in clinic. Any patients that are deemed by the principal investigator or co-investigators to be mentally or physically incapable of consent will not be included in the study.

SBRT ADMINISTRATION AND RADIATION TREATMENT PLANNING

Pre-Linac based SBRT Tests, Procedures, and Planning

The following will be completed prior to Linac based SBRT:

- Signed informed consent document.
- Medical history and clinical examination.
- CBC with differential, Chemistry Panel, CA19-9.
- Gold fiducial seed placement percutaneously, intraoperatively, or under endoscopic ultrasound guidance, technique will be determined clinically. Fiducial placement may be performed prior to enrollment.

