- Pathologic confirmation of malignancy. (Core biopsies during gold fiducial placement as needed or optional). Patients are encouraged but not required to have tissue banked in UCCI Tumor Bank per Tumor Bank protocol.
- Pancreas protocol CT required; if patient allergic to contrast and allergy can not be premedicated with steroids prior to IV contrast, pancreas protocol MRI will be obtained
- Baseline collection of EORTC QLQ C-30/ PAN26 QOL.

Fiducials

Treatment on this protocol requires placement of 1-5 gold (99.9% pure, 1-5 mm length, or visicoils) fiducials for targeting purposes. The fiducials will be used as surrogates for targeting the daily tumor position during treatment. The fiducials will be placed directly into the tumor and/or periphery under endoscopic ultrasound or CT guidance. When possible, clips or fiducials will also be placed in the proximal duodenum directly adjacent to the pancreatic tumor. Fiducials may be implanted prior to enrollment as this is an acceptable standard of care procedure for any patient receiving radiotherapy for pancreatic cancer.

If fiducials are not placed intraoperatively and/or prior to enrollment, placement will be done and is expected to be done on an outpatient basis. In rare occurrences when fiducials/clips cannot be placed, patients may be treated at the discretion of the PI.

Simulation

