- Creatinine clearance >60 mL/min/1.73 m² for patients with creatinine levels above institutional normal
- Ability to understand and the willingness to sign a written informed consent document.
- Patients are to have received neoadjuvant chemotherapy prior to enrollment (3-4 months). Approved regimens may consist of 3-4 months of gemcitabine-based chemotherapy or FOLFIRINOX. Patients will have a 2-4 week break between last chemotherapy

administration and start of SBRT.

- Patient must be able to have fiducials placed. If not, the tumor must be posterior and adjacent to the aorta and treatment will only be permitted at the discretion of the Principal Investigator.

Exclusion Criteria

- Children (< 18 years) are excluded because pancreatic tumors rarely occur in this age group. Furthermore, treatment requires a great deal of patient cooperation including the ability to lie still for several hours in an isolated room.
- Uncontrolled intercurrent illness including, but not limited to, ongoing or active infection (or infections requiring systemic antibiotic treatment), symptomatic congestive heart failure, unstable angina pectoris, cardiac arrhythmia, or psychiatric illness/social situations that would limit compliance with study requirements.
- Pregnant and breastfeeding women are excluded as are women of child-bearing potential who are unwilling or unable to use an acceptable method of birth control (hormonal or barrier method of birth control; abstinence) to avoid pregnancy for the duration of the study treatment. Should a woman become pregnant or suspect she is pregnant while undergoing radiotherapy in this study, she should inform her treating physician immediately.
- Women who are not post-menopausal (as defined in Appendix V) and have a positive urine or serum pregnancy test or refuse to take a pregnancy test.

VI. RISK / BENEFIT

Risk Information

It is difficult at this time to predict with confidence the percentage rate of complications from the proposed Linac based SBRT treatment. However, it is reasonable to extrapolate from the current experience with radiotherapy in and around the pancreas. Based upon prior phase I and phase II studies, we anticipate that the toxicities associated with this treatment will be acceptable.

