- Follow-up Evaluations including H&P, Review of Systems, and toxicities
- Follow-up labs and dates
- Completion of QOL questionnaires
- Subject study withdrawal, date, and reason
- Concomitant medications, specifically PPIs and anti-emetics, prescribed per protocol and if reportedly taken by subject

Confidentiality

Study data will be maintained in password protected computer files. Only research personnel listed on this protocol will have access to this information. Only the patients unique IDN will be used. The patient's name or other public identifiers will not be included in any information shared with other investigators. The study data with identifiers will be kept at in Oncore.

XI. CORRELATIVE STUDIES

Correlative studies to develop predictive and prognostic information will focus on molecular markers of interest in pancreatic cancer. For all of the markers described below, tissue from both pre-treatment biopsies and post-resection specimens will be subjected to immunohistochemical (IHC) analysis. Funding for correlative studies will come from either pending grant applications or

supported by the UCCI GI Center of Excellence.

Differential expression of these markers correlated with clinical outcomes can provide invaluable prognostic data, as well as a basis for future clinical trials with a personalized, molecular profile-targeted approach. The markers of interest are:

Hyaluronan- Tumor stroma microenvironment has been very important in pancreas cancer. The interstitial pressure is very high, which limits the diffusion of chemo and blood flow in the tumor¹⁰. Hyaluronan (HA) is one component of the stroma thought to be responsible for this and HA can be evaluated by IHC. Hyaluronan inhibitor (PEGPH20) is currently under investigation in metastatic pancreatic cancer and HA could potentially be used as a radiosensitizer. This would be a completely new mechanism of sensitization. We would plan to evaluate HA concentration by IHC, and would consider decreased post-SBRT concentration as a preliminary indicator that SBRT has some synergy with HA inhibition warranting further study.

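### Section XI reads a fall in hyaluronan as a sign of an SBRT effect, but does not require the baseline tissue to be taken after chemotherapy

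*Combined protocol and SAP*

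**What the plan says.** The opening of Section XI sets the specimens for the tissue markers: "tissue from both pre-treatment biopsies and post-resection specimens will be subjected to immunohistochemical (IHC) analysis". The term *pre-treatment* is not defined relative to chemotherapy. The Hyaluronan paragraph then says that the investigators "would consider decreased post-SBRT concentration as a preliminary indicator that SBRT has some synergy with HA inhibition warranting further study".

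Chemotherapy and biopsy timing are set elsewhere:

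- Section IV, Registration Procedures: "Patients will have chemotherapy (3-4 months) for pancreas cancer prior to study enrollment".
- Section V, Inclusion Criteria: "Approved regimens may consist of 3-4 months of gemcitabine-based chemotherapy or FOLFIRINOX". The same criterion asks for 2-4 weeks between the last chemotherapy and the start of SBRT.
- Synopsis, Procedures: "Endoscopically guided fiducial placement with optional biopsies obtained at the time of fiducial placement".
- Section IV, Pre-Linac based SBRT Tests: "Core biopsies during gold fiducial placement as needed or optional". The same list adds: "Fiducial placement may be performed prior to enrollment".
- Appendix I, Study Calendar: the biopsy row is marked once, under Pre-Study. Seed placement is marked under Pre-SBRT, where footnote 8 allows a 45-day window before treatment.

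In the other tissue paragraphs of Section XI, D1R is to be assessed in tissue from before and after SBRT, and phosphatidylserine (PS) in core biopsies from before SBRT and in resection specimens. Neither paragraph says how a change would be interpreted.

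**The concern.** The HA sentence attaches a conclusion about SBRT to a before/after difference. That attribution needs a baseline at which SBRT is the only treatment still to come before resection. The plan does not secure this. Tissue obtained before or during chemotherapy satisfies the wording of Section XI, and the change from it to resection includes whatever chemotherapy did to the marker. The trial has one arm, and Section XI plans no chemotherapy-only comparison and no adjustment, so the analysis itself cannot separate the two.

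What is at stake is a decision to pursue HA inhibition combined with SBRT because of a fall that chemotherapy may have produced. The error could also run the other way: if chemotherapy raised HA, a real fall after SBRT could be hidden.

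**Working it through.** The documents give no sample size, effect size, test or threshold for the marker comparison, so there is no figure of the plan's own to reproduce. The check covers timing, then the consequence of a rule whose only criterion is a decrease.

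**1. Interval if the baseline precedes chemotherapy**

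Inputs: chemotherapy 3-4 months (Sections IV and V); break 2-4 weeks (Section V); SBRT over 15 days and surgery 4-6 weeks later (Synopsis, Treatment). One month is 365.25/12/7 = 4.348 weeks; 15 days is 2.14 weeks. The biopsy is assumed to fall immediately before the first cycle, so these are minimum intervals.

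| | Short case | Long case |
|---|---|---|
| Chemotherapy (weeks) | 3 × 4.348 = 13.04 | 4 × 4.348 = 17.39 |
| Break | 2 | 4 |
| SBRT | 2.14 | 2.14 |
| SBRT to surgery | 4 | 6 |
| Total | 21.19 | 29.54 |
| Chemotherapy share | 13.04/21.19 = 62% | 17.39/29.54 = 59% |
| Share before first fraction | 15.04/21.19 = 71% | 21.39/29.54 = 72% |

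A shorter SBRT course, which calendar footnote 10 describes, would raise both shares.

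**2. Whether a fiducial-placement biopsy guarantees a post-chemotherapy baseline**

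The Pre-SBRT window is 45 days; the break is 14 to 28 days.

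- 4-week break: 45 − 28 = 17 days.
- 2-week break: 45 − 14 = 31 days.

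A biopsy inside the permitted window can therefore precede the last chemotherapy dose by up to 17 to 31 days. Placement before enrollment is also allowed, and chemotherapy is given before enrollment.

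**3. Number of pairs**

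Section IX caps enrollment at 20, and its completion rule is still met with 6 resected patients. With the rule met, 6 to 20 patients would have a resection specimen. The number of pairs may be lower, because the biopsy at fiducial placement is optional and Section V allows entry without histology in some cases.

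**4. Illustration: no SBRT effect at all**

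Assumptions, none from the documents: every baseline precedes chemotherapy, paired changes are normal, chemotherapy lowers HA by d standard deviations of the paired change, and the criterion is applied to the mean change over n pairs. The chance that the mean is lower at resection is Φ(d√n).

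| d | n = 6 | n = 12 | n = 20 |
|---|---|---|---|
| 0 | 50% | 50% | 50% |
| 0.25 | 73% | 81% | 87% |
| 0.5 | 89% | 96% | 99% |

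For example, d = 0.25 and n = 6 gives Φ(0.25 × 2.449) = Φ(0.612) = 0.73. With a chemotherapy shift in this direction, more pairs make the misattribution more likely. With no shift at all, the criterion is still met half the time, because no threshold is set.

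**The case against.** **The protocol generally uses *treatment* to mean SBRT.** The acute toxicity window runs from SBRT, and in Section XII the pretreatment CT is the one used for radiation planning. This is a fair reading, and it counts against any suggestion that a pre-chemotherapy baseline was intended. It does not close the gap, because a biopsy taken before chemotherapy is also before SBRT.

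**The confounded pair is possible, not documented.** A reader might infer that a patient without the optional biopsy must be compared using diagnostic tissue from before chemotherapy. The documents do not support that: they neither date the diagnostic biopsy nor name it as fallback tissue, and such a patient may simply contribute no pair. What stands is that nothing excludes such a baseline.

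**Only HA carries the inference.** A reader might extend the charge to D1R and PS. Both share the unclear specimen timing, but neither has a rule crediting SBRT, and the PS text names core biopsies, which fits the fiducial-placement cores. The circulating tissue factor work uses blood, so the biopsy point does not apply to it.

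**The work is exploratory.** The HA reading is called preliminary, part of the funding is pending, and no marker enters the feasibility decision in Section IX. This stands in full and limits the weight of the point.

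**The dates are already collected.** Section X (Data Entry and Compilation) captures dated procedures, including biopsy and seed placement, and the schedules of earlier chemotherapy. This also stands. What is missing is a rule that uses them.

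**Conclusion.** The point holds for HA. The plan states how a fall will be read, and that reading is not secured by the specimens it permits: baseline tissue taken before or during chemotherapy would yield a change over chemotherapy plus SBRT. For D1R and PS only the ambiguity of specimen timing holds.

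The size cannot be stated as a number of patients; from the documents it could be anywhere from none to all of the pairs. The 59-62% and 71-72% are shares of calendar time and rest on a biopsy just before the first cycle. They should not be read as shares of the marker change, and nothing in the documents shows that chemotherapy alters HA, D1R or PS. The probabilities in the illustration depend on assumed shifts.

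No endpoint, safety rule or phase II decision criterion is affected. This is a cheap improvement to what the HA analysis can claim.

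**What to change.** In Section XI:

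- Base any statement about an SBRT effect on HA, and any such statement made for D1R or PS, only on pairs whose baseline tissue was collected after the last chemotherapy dose and before the first SBRT fraction.
- Classify each pair by the actual collection date, using the procedure and chemotherapy records that Section X already captures. Do not classify by whether the biopsy was taken at fiducial placement, since that does not establish its order relative to chemotherapy.
- Report all other pairs separately, as change over chemotherapy plus SBRT, with the number of pairs in each group.

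The cost is a few sentences and fewer pairs for the SBRT-specific comparison, possibly very few. No extra biopsy and no change to treatment is needed. Even the restricted pairs have no control group, so the conclusion should stay preliminary.
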